The FRESH cohort consists of HIV-uninfected young women age 18-23 living in Umlazi, South Africa. In this region, <1% of 14 year old girls are HIV positive but over 60% of 24 year old women are HIV infected.  Since the study inception in 2012, over 1400 women have been enrolled. FRESH follows women for 9-months with twice weekly HIV viral load PCR testing. Paired blood and genital mucosal sampling occurs every three months with specific collection of cervical and vaginal swabs, cervical cytobrush and cervicovaginal lavage (CVL). Questionnaires are collected at each visit detailing symptomatic and sexual behavior data, diet, vaginal hygiene practices, contraceptive use, medical history and demographic factors. All participants undergo regular STI testing. Currently, over 6,000 CVL and cytobrushes, and 13,000 swabs have been stored from the study. We have also begun to culture, store, perform whole genome sequencing (WGS) on bacterial isolates to provide a detailed characterization of genomic and strain level variation within the cervicovaginal microbiome of these participants. Enrolment is ongoing with 300 new participants enrolled each year. Baseline characterization of cervicovaginal bacterial communities by 16s rRNA gene sequencing is performed on all participants.

Women who have a non-*Lactobacillus*-dominant vaginal microbiota community type and meet the inclusion and exclusion criteria will be offered enrolment in the LACTIN-V trial.

Funding for the core sample collection in FRESH has been secured from the Bill & Melinda Gates Foundation, Gilead Sciences Inc., and the Ragon Institute to cover the funding period of this grant proposal. Therefore, this study leverages an existing major site investment to enrol female participants, characterize their baseline vaginal microbiome and mucosal immune factors and perform detailed analysis on specimens collected as part of this cohort. There is no overlap between the work in this proposal and any other grants. The proposed Phase 2 trial of LACTIN-V within the FRESH cohort provides an unprecedented opportunity to study the effects of a *L. crispatus* on host-microbial interactions and genital tract inflammation.

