#### 3.4 Study Outcome Measures

#### 3.4.1 Primary/ Secondary Outcome Measures

# *Primary / Secondary Outcome Measures for Objective 1 (effect on genital tract proinflammatory cytokines and HIV target cells)*

The proportion of participants with decreased genital tract proinflammatory cytokines and HIV target cells at 6 and 10 weeks of follow up, compared to levels at the baseline FRESH Study Visit, and Randomization Visit on Day 8 of the study (after treatment with Metronidazole is completed).

Our outcome will be a change after 4 weeks of treatment with LACTIN-V in comparison to

placebo, for the following:

- i. a decrease of the concentrations of proinflammatory cytokines in genital fluid that have been associated with risk for HIV acquisition,
- ii. a decrease in the number of activated HIV target cells (i.e. CD4+/CCR5+/HLA-DR+/CD38+ T cells) in the endocervix and
- iii. an increase the anti-HIV effect of vaginal secretions relative to placebo.

*Primary / Secondary Efficacy Outcome Measures for Objective 2 (promoting Lactobacillusdominant microbiota)* 

1:

The proportion of participants with increased *Lactobacillus*-dominant vaginal microbiota in young South African women, compared to levels at randomization (Day 8) after completion of metronidazole. Measured will be overall *Lactobacillus* species, as well as *Lactobacillus crispatus*, *Lactobacillus jensenii*, *Lactobacillus gasseri*, and *Lactobacillus iners*.

Our primary outcome is the presence of *Lactobacillus*-dominant vaginal microbial cervicotypes after 4 weeks of treatment with LACTIN-V, and following the post- dosing phase at Day 64.

Secondary outcomes include comparison of *L. crispatus* vs. *L. iners* prevalence between treatment groups, persistence of colonization after stopping therapy, effect of sex and/or vaginal hygiene practices on colonization by lactobacilli, and stability of vaginal microbial communities over time in the treatment vs. placebo group.

2:

The proportion of participants with a positive BV diagnosis in each study arm by Day 64.

BV is defined Nugent score 7-10. Following FDA guidance all BV diagnoses during follow-up visits are considered incident, as they occur at least 22-30 days after the commencement of Metronidazole treatment and consequently are treatment failures or new infections. For the purpose of this trial, treatment failure and new infection will both be considered recurrent BV.

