## 4.0 STUDY DESIGN

This is a Phase 2 randomized double-blind placebo-controlled trial to assess the impact of the live biotherapeutic product LACTIN-V containing *Lactobacillus crispatus* CTV-05 on the vaginal microbiome of young women in South Africa at high risk of HIV acquisition.

The study will also assess the safety of LACTIN-V by comparing the incidence of AEs between women randomized to LACTIN-V or placebo.

We will conduct a randomized, placebo-controlled trial of LACTIN-V in a cohort of young South African women with a non-*Lactobacillus* dominant microbiota, who are sexually experienced, age 18 to 23 years. Enrolment will be continued until 60 women will be randomized into the study.

Eligible women will be treated with oral metronidazole 400 mg twice daily for seven days and will then be randomized 2:1 to LACTIN-V vs. placebo.

Within 8-48 hours of taking the final metronidazole dose, women will receive the study product for five consecutive days, followed by a twice weekly dose for three additional weeks.

After enrolment and metronidazole treatment, women will be followed throughout the 4 weeks of dosing and the 4 weeks of post-dosing phase for a total of 10 weeks (until approximately Day 64).

The primary outcome (**Objective 1**) focuses on the ability of the *L. crispatus* CTV-05 to acutely decrease genital tract inflammation (as a marker of HIV susceptibility). This will be assessed by collecting cervicovaginal fluid and endocervical immune cells at randomization (Day 8), after 4 weeks of treatment with the LACTIN-V vs. placebo (Day 36), and after 4 weeks of post-dosing phase (Day 64).

Direct anti-HIV activity will be assessed with *in vitro* HIV infection assays using vaginal fluid samples from randomization and after treatment: Randomization Visit (Day 8), Follow-up Visit (Day 36), and Final Visit at Day 64.

A secondary outcome (**Objective 2**) is to assess the ability of the *L. crispatus* CTV-05 to establish durable vaginal colonization as with the potential as a self-sustaining prevention strategy. This will be assessed by characterization of the vaginal microbiome at the baseline FRESH Study Visit, and the end of treatment (Day 36) and at the Final Visit (Day 64), after 4 additional weeks during the post-treatment phase.

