At the **Enrolment Visit 1 (Day 1)**, participants will complete a medical history and undergo a physical examination. Enrolled participants will receive oral Metronidazole 400mg tablets, and are instructed to immediately start the 7-day course (twice daily), to be completed within 8-48 hours of the Randomization Visit on Day 8. A **Check-In Visit 2 (Day 4)** is scheduled to provide additional guidance for the metronidazole administration.

At the **Randomization Visit 3 (Day 8)**, a gynaecological exam will be conducted to collect baseline vaginal microbiome data, including cervical swabs, cervicovaginal lavage fluid and an endocervical cytobrush to assess the microbial composition, cytokines and mucosal HIV target cells. A gram stain and a vaginal swab for *L. crispatus* (including CTV-05) identification will be collected. Only participants who completed their 7-day course of oral Metronidazole will be randomized and receive study product.

The 11 doses of LACTIN-V at 2 x 10^9 cfu/dose or placebo are scheduled to be administered by vaginal applicator for 5 consecutive days and then twice weekly for 3 weeks, throughout Week 1-4 of the study. The first dose of study product is administered as part of the Randomization Visit on Day 8. Participants will be instructed to take the second and third dose on subsequent Days 9 and 10 at home before bedtime. All other doses will remain at the clinic site, where the women are attending regular twice-weekly visits as participants of the FRESH study. During these FRESH visits, they will be handed the remaining LACTIN-V applicators to administer on site according to schedule in a form of directly observed therapy.

During the study, participants will be counselled to use the provided lubricated or unlubricated nonspermicidal condoms during vaginal intercourse. Study staff will provide condoms that have been tested to not interfere with lactobacilli growth. In addition, participants are counselled to avoid vaginal intercourse during the 12 hours before scheduled gynaecological exams, as this activity could lead to microabrasions notable at speculum exam, and could interfere with a correct determination of symptoms related to study product administration. Further, participants will be counselled to avoid sexual intercourse for 12 hours after study product administration to ensure that the product will remain inside the vagina.

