# 11.2 Study Objectives and Outcome Measures

As described in section 3.2 and 3.3, the primary study objectives are to compare LACTIN-V with placebo following a 7-day treatment course with Metronidazole with respect to safety and impact on the vaginal microbiome, specifically *lactobacillus* growth and decrease in pro-inflammatory cytokines and HIV target cells.

In Objective 1, the outcomes of interest will be:

(1) a decrease in genital tract inflammation from baseline (the FRESH Study Visit before enrollment) to Day 36 Follow-Up Visit, as defined by a  $\geq$ 1 Log10 decrease in the concentration of cytokines that have been associated with an increased risk for HIV infection., and

(2) the change in the concentration of cytokines at the Final Visit on Day 64 (4 weeks after dosing phase completed) compared to baseline, number of endocervical CD4+ HIV target cells at Day 36 Follow-Up and Day 64 Final Visits compared to baseline, and in vitro anti-HIV activity of cervicovaginal lavage at Day 36 Follow-Up and Day 64 Final Visits. We will compare each outcome by study arm.

In Objective 2, the outcomes of interest will be:

(1) the presence of *Lactobacillus*-dominant vaginal microbial cervicotypes at the Day 36 Follow-Up Visit, and following the post-dosing phase at the Day 64 Final Visit in the LACTIN-V arm; and

(2) the comparison of *L. crispatus* vs. *L. iners* prevalence between treatment groups, quantity of vaginal *L. crispatus*, presence of the specific CTV-05 *L. crispatus* strain, persistence of colonization after stopping therapy, effect of sex and/or vaginal hygiene practices on colonization by lactobacilli, and stability of vaginal microbial communities over time in the treatment vs. placebo arms.

In Objective 3, the outcomes of interest will be:

- (1) the proportion of treatment related adverse events study arm, in particular Grade 3 AEs; and
- (2) the proportion of participants finding the product acceptable and are willing to use it Page 64 of 124

should it become commercially available, as measured in a standardized acceptability questionnaire.

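### The reference visit for the primary cytokine responder endpoint is inconsistent across sections, and no section states the endpoint in full

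*Combined protocol and SAP*

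**What the plan says.** The pieces of the primary endpoint are spread over five sections.

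- **11.2** gives the Objective 1 outcome as "a decrease in genital tract inflammation from baseline (the FRESH Study Visit before enrollment) to Day 36 Follow-Up Visit", with a threshold of 1 log10. It does not mention 3 of 9 cytokines.
- **3.4.1** speaks of levels "compared to levels at the baseline FRESH Study Visit, and Randomization Visit on Day 8 of the study", after metronidazole. It joins the two visits without ranking them. It then adds "Our outcome will be a change after 4 weeks of treatment with LACTIN-V in comparison to" placebo, which reads more naturally as a change starting at Day 8.
- **4.0**, for Objective 1, says "This will be assessed by collecting cervicovaginal fluid and endocervical immune cells at randomization (Day 8), after 4 weeks of treatment" and again at Day 64. The FRESH visit is not listed. The description of the Day 8 visit in the same section refers to "baseline vaginal microbiome data, including cervical swabs, cervicovaginal lavage fluid and an endocervical cytobrush to assess the microbial composition, cytokines" and target cells. For Objective 2, however, 4.0 attaches the word baseline to the FRESH visit.
- **11.3** is the only section with the 3-of-9 rule. It names lavage specimens and Day 36 as the assessment visit, but not the visit from which the decrease is measured. The 10% placebo and 50% LACTIN-V rates are stated there.
- **11.5** applies Fisher's exact test to the proportion with a decrease of at least 1 log10. It gives neither a reference visit nor the 3-of-9 rule.

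Lavage appears to be available at both visits. Section 2.5 includes it in FRESH mucosal sampling, 7.1 says the Week 5 FRESH visit includes mucosal sampling, and 7.3 lists a lavage sample on Day 8.

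**The concern.** An analyst who follows the protocol faithfully could score each woman's response from either visit. The two scores measure different things. One starts before a seven-day antibiotic course that every woman takes, and the other starts after it. A woman can be a responder on one score and not on the other. With 20 and 40 women per arm, a few changes of status can alter the primary 2x2 table.

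Two things are at stake. The choice of reference visit is left open until the data can be seen. The 10% and 50% rates behind the sample size are also not tied to a stated starting point, so a reader cannot judge whether they are plausible.

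**Working it through.** **1. The plan's own figure.** Inputs from 11.3: 20 placebo and 40 LACTIN-V women, 10% versus 50% responders, two-sided Fisher's exact test at 5%. Summing the binomial probabilities of every 2x2 table with p ≤ 0.05 gives power 0.891. A run of 10,000 Monte Carlo samples also gives 0.891. The stated figure of more than 88% is reproduced.

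**2. Which part of the endpoint stands where.**

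| Section | Reference visit | 1 log10 | 3 of 9 | Lavage | Day 36 |
|---|---|---|---|---|---|
| 3.4.1 | FRESH and Day 8, unranked | no | no | no | as 4 weeks of treatment |
| 4.0 (Objective 1) | Day 8 listed, FRESH not | no | no | cervicovaginal fluid | yes |
| 11.2 | FRESH | yes | no | no | yes |
| 11.3 | none | yes | yes | yes | yes |
| 11.5 | none | yes | no | no | no |

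No row is complete. The only section with the 3-of-9 rule has no reference visit.

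**3. How the two scores differ.** Let F, E and D be the log10 level of a cytokine at FRESH, Day 8 and Day 36. The fall from FRESH is F − D and the fall from Day 8 is E − D. Their difference is (F − D) − (E − D) = F − E, the FRESH-to-Day 8 change. That change contains whatever metronidazole effect is present by Day 8. Any later waning or resurgence acts on D and so enters both scores.

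The intervals follow from 4.0 and 7.5. Enrolment (Day 1) is 7 to 30 days after the FRESH visit, and Day 36 is 35 days after Day 1, so FRESH to Day 36 is 42 to 65 days. With the Day 33–43 window it is 7 + 32 = 39 to 30 + 42 = 72 days. Day 8 to Day 36 is 28 days, or 25 to 35 with the window.

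**4. Illustration of size.** The documents give no responder rates by visit, so the following inputs are assumed. The fall in each of the 9 cytokines is normal with SD 0.5 to 0.8 log10, with the same correlation between every pair of cytokines, 0.3 to 0.7. The mean falls are solved so that P(at least 3 of 9 fall by 1 log10 or more) equals 10% and 50%. At SD 0.6 and correlation 0.5 they are 0.16 and 0.76 log10. Let m be the mean FRESH-to-Day 8 fall. Changing the reference visit subtracts or adds m, and exact Fisher power is recomputed with 20 and 40 women.

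| Planned rates hold from | Scored from | m | Rates at SD 0.6, correlation 0.5 | Power there | Power over the range |
|---|---|---|---|---|---|
| FRESH | Day 8 | 0.1 | 6.7% vs 41.4% | 0.84 | 0.81–0.86 |
| FRESH | Day 8 | 0.25 | 3.4% vs 29.4% | 0.72 | 0.53–0.80 |
| Day 8 | FRESH | 0.1 | 14.3% vs 58.6% | 0.91 | 0.91–0.92 |
| Day 8 | FRESH | 0.25 | 22.9% vs 70.6% | 0.93 | 0.92–0.94 |

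Under this model, which uses the same SD of change for both scores, m = 0 gives the same expected rates and power from either visit.

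**5. A separate point on the level comparisons.** Section 11.5 also compares cytokine levels between arms and names two-sample t and Wilcoxon tests as examples. Adjusting for a covariate with correlation ρ to the outcome makes n women worth about n/(1 − ρ²). With n = 60 and assumed ρ of 0.3, 0.5 and 0.7, this gives 60/0.91 = 66, 60/0.75 = 80 and 60/0.51 = 118.

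**The case against.** The strongest reply is that 11.2 already settles the matter. It is the only explicit definition in the statistical section and it stands directly before the sample size. Sections 3.4.1 and 4.0 also use the word baseline for the FRESH visit, while 3.4.1 calls Day 8 the randomisation visit. The phrase in 4.0 that calls the Day 8 data baseline describes sample collection and does not define an endpoint. All of this stands, and it makes FRESH the documented default. It is therefore too strong to say that the plan contains rival definitions of equal standing. What remains is that nothing says 11.2 overrides the other sections, and that 11.2 does not define the 3-of-9 endpoint on which the trial was powered.

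A reader might infer that one of the choices biases the arm comparison. It does not, because both visits precede randomisation.

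A reader might also infer that a change from Day 8 is free of metronidazole effects. That goes too far. Section 2.2 reports relapse within 1 to 3 months after standard antibiotic treatment, and 2.4 describes resurgence of BV-associated bacteria by Day 28 in women who did not colonise. Such late changes fall inside the Day 8 score as well. For the same reason, the power illustration does not need the metronidazole effect to last to Day 36.

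On the level comparisons, unadjusted tests are valid under randomisation, 11.5 offers them only as examples, and it already plans mixed models or GEE. Adjustment is a gain in precision and corrects no error.

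**Conclusion.** The inconsistency is real and should be fixed, but it is limited. The powered endpoint lacks a single complete definition, and its reference visit differs or is missing across 3.4.1, 4.0, 11.2, 11.3 and 11.5. FRESH is the better-supported reading. There is no bias, no wrong power figure, and no reason to change the sample size or the test. The harm is that the primary table could be scored either way after the data are seen, and that the 10% and 50% rates have no stated reference.

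A reader might take the power range of 0.53 to 0.94 as evidence that the trial is underpowered. The documents do not support that. The range rests on an assumed FRESH-to-Day 8 fall of 0.1 or 0.25 log10 and on assumed standard deviations and correlations. It shows only that the choice of visit could matter. The share of women who would change status between the two scores cannot be derived from the documents either, because they give no variability for the cytokines.

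One limit applies: Appendix D, on coordination with FRESH, appears by title only, so the handling of the FRESH lavage specimen could not be checked there.

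**What to change.** 1. Write the complete endpoint once: reference visit, lavage specimen, decrease of at least 1 log10, at least 3 of the 9 cytokines, Day 36. Keep the FRESH visit of 11.2 as the primary reference unless the sponsor changes it to Day 8 before unblinding. Use the same definition in 3.4.1, 4.0, 11.2, 11.3 and 11.5. Label the change from the other visit a sensitivity analysis. State in 11.3 that the 10% and 50% rates refer to the chosen reference.

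2. As a separate improvement that leaves the Fisher responder test untouched, compare Day 36 log10 cytokine levels between arms in 11.5 by ANCOVA with the Day 8 value as covariate, in place of the unadjusted t or Wilcoxon tests. Keep a rank-based analysis as sensitivity.

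The cost is wording and a little analysis work. No new samples, visits or participants are needed. The trial gives up only the freedom to choose the reference visit later.

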Our Phase 2b clinical trial of LACTIN-V to prevent recurrent BV (NCT02766023) completed follow-up in February 2019. The trial was designed to provide a screening evaluation for the hypothesis that, following a 5-day treatment with MetroGel® (topical metronidazole) to treat BV, LACTIN-V administered at 2 x 10^9 cfu/dose using a vaginal applicator reduces the 12week incidence of BV recurrence when compared to placebo. The primary objectives of this study were: 1) to estimate the efficacy of 5 daily doses in week 1 followed by twice weekly dosing in weeks 2-11 of LACTIN-V (2 x 10^9 cfu/dose) as compared to placebo in preventing BV recurrence by 12 weeks following treatment of BV with MetroGel; 2) to assess the safety of LACTIN-V over 24 weeks by comparing the incidence of AEs between individuals randomized to LACTIN-V or placebo. A total of 228 women underwent randomization: 152 to the Lactin-V group and 76 to the placebo group; of these participants, 88% in the Lactin-V group and 84% in the placebo group could be evaluated for the primary outcome. In the intention-to-treat population, recurrence of bacterial vaginosis by week 12 occurred in 46 participants (30%) in the Lactin-V group and in 34 participants (45%) in the placebo group (risk ratio after multiple imputation for missing responses, 0.66; 95%.

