#### 4:

The proportion of subjects with cervicotypes I-IV compared by study arm.

Primary / Secondary Outcome Safety Measures for Objective 3 (safety and acceptability)

Safety of LACTIN-V and the applicator will be measured by:

The proportion of participants reporting product-related AEs and SAEs through the final visit that are likely related to use of study product compared by study arm, in particular Grade 3 AEs and SAEs.

Acceptability of LACTIN-V and the applicator will be measured by standardized questionnaire about acceptability of the study product and participants' stated willingness to use this type of product in the future, in each study arm.

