# 11.5. Statistical Analysis Plan

The primary analyses in Objective 1 is to compare the levels of i) pro-inflammatory genital tract cytokines levels & proportion of subjects with a significant decrease ( $\geq 1 \log_{10}$ ) in cytokines levels, ii) HIV target cells (i.e., CD4+/CCR5+/HLA-DR+/CD38+ T cells) and iii) anti-HIV effect of CVL, as assessed by HIV p24 levels, between the two treatment arms.

Graphical and descriptive measures (such as frequency, percent mean, median, standard deviation and IQR) will be used to summarize data. Spearman rank correlation will be used to examine associations among the aforementioned outcomes. Statistical tests (such as the two sample T and Wilcoxon rank sum tests) will be used to compare levels of cytokines, HIV p24 levels and HIV target cells between the two treatment groups.

For within group comparison, statistical tests (such as paired T and Wilcoxon signed rank tests) will be used. Longitudinal data analyses using nonlinear mixed models or generalized estimating equations will be performed to examine and compare the overtime changes in cytokines levels and HIV target cells. Fisher's exact test will be used to compare the proportion of subjects with a significant decrease ( $\geq 1 \log_{10}$ ) in cytokines levels.

Data classification and dimension reduction techniques (e.g., principal component analysis, and cluster analysis) will be used to group a set of cytokines or HIV target cells to uncorrelated summary variables or to identify study subjects with similar cytokine or HIV target cell profiles. Adjustment will be made for multiple comparisons using less conservative multiple testing correction procedures (such as the Holm's and Benjamini-Hochberg methods) where appropriate.

The primary analysis in Objective 2 is to compare the presence and abundance of *Lactobacillus spp*. (including *L. crispatus* CTV-05) between the two study groups. As in Objective 1, graphical and descriptive measures will be used to summarize data. Fisher's exact test will be used to compare presence of specific strains of vaginal lactobacilli and cervicotypes (CT). Empirical Bayes method will be used for identification of microbes that show differential abundance between study arms. Empirical Bayes method is more efficient due to its ability of pooling information across microbes.

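### The main outcome of Objective 2 (Lactobacillus dominance) is defined differently in sections 3.4.1, 11.2 and 11.5, and section 4.0 disagrees with 3.3.1 on whether it is primary

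*Combined protocol and SAP*

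**What the plan says.** Section 3.3.1 lists promotion of a Lactobacillus-dominant vaginal microbiota as the second of three primary objectives. The outcome behind it is then described in several ways.

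- **Section 3.4.1, Objective 2, measure 1, opening sentence:** the proportion of women whose dominance has increased, "compared to levels at randomization (Day 8) after completion of metronidazole". No size of increase is given, and nothing is said about women already dominant on Day 8.
- **Section 3.4.1, same measure, next paragraph:** "Our primary outcome is the presence of" Lactobacillus-dominant cervicotypes after four weeks of treatment and at Day 64. No comparator is named.
- **Section 3.4.1, measure 4:** "The proportion of subjects with cervicotypes I-IV compared by study arm".
- **Section 11.2, lead-in:** "the primary study objectives are to compare LACTIN-V with placebo following a 7-day treatment course with Metronidazole".
- **Section 11.2, Objective 2, outcome (1):** presence of such cervicotypes at Day 36, and "following the post-dosing phase at the Day 64 Final Visit in the LACTIN-V arm". Between-arm wording appears only under outcome (2).
- **Section 11.5:** "The primary analysis in Objective 2 is to compare the presence and abundance of" Lactobacillus species between the two groups. Cervicotypes come in only through the sentence on Fisher's exact test, and no visit is named.
- **Section 4.0:** Objective 2 is called a secondary outcome. Its microbiome time points are the FRESH baseline visit, Day 36 and Day 64. Day 8 is not among them, although Day 8 samples are planned in the same section and in 7.3.

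**The concern.** These texts do not describe one quantity. They differ on whether the outcome is a state or a change, on which arms it covers, on the visit, on whether it concerns a dominant cervicotype or any Lactobacillus, and on its rank.

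The arm wording matters because the outcome is not specific to the product. Section 3.4.1 counts L. iners among the lactobacilli measured, and section 2.3 describes a cervicotype dominated by L. iners, so a woman can meet the outcome without CTV-05. All women take metronidazole before randomization (section 3.2). Section 2.5 reports that dominance rose in a Kenyan trial of monthly antibiotic treatment without any live product, though the gain did not last. A rate from the LACTIN-V arm alone cannot separate recovery after antibiotics from a product effect.

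The choice between presence and increase matters because the two can classify the same woman differently. If increase means not dominant on Day 8 and dominant later, a woman dominant at both visits succeeds under one wording and fails under the other. With several wordings in the text, the choice could be made after the data are seen.

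**Working it through.** **1. The plan's own figure.** The only power statement is in section 11.3 and concerns the Objective 1 cytokine endpoint: 10% vs 50%, 20 placebo and 40 LACTIN-V women, two-sided Fisher's exact test at 5%, power above 88%. Summing the binomial probabilities of all 21 × 41 possible outcomes with Fisher p ≤ 0.05 gives 0.891, so the figure reproduces. The plan gives no rate, effect size or power for Objective 2, so the inputs below are assumptions.

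**2. What a LACTIN-V-only rate can show.** Assume 24/40 = 60% dominant on LACTIN-V (exact 95% CI 43% to 75%). Read literally, 11.2(1) would report nothing more. The same 24/40 set against possible placebo results:

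| Placebo | Difference (points) | Fisher p |
|---|---|---|
| 2/20 (10%) | 50 | 0.0002 |
| 4/20 (20%) | 40 | 0.0055 |
| 6/20 (30%) | 30 | 0.054 |
| 8/20 (40%) | 20 | 0.18 |
| 12/20 (60%) | 0 | 1.00 |

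**3. Presence against increase.** Let q be the share already dominant on Day 8, equal in both arms because Day 8 samples precede the first dose. Read increase as not dominant on Day 8 and dominant on Day 36. Assume true presence on Day 36 of 60% on LACTIN-V and 30% on placebo.

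*Day 36 status independent of Day 8 status.* The increase rate is (1 − q) × presence rate:

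| q | LACTIN-V | Placebo | Difference (points) | Power (Fisher, 40 vs 20) |
|---|---|---|---|---|
| 0 (same as presence) | 60% | 30% | 30 | 0.51 |
| 0.10 | 54% | 27% | 27 | 0.43 |
| 0.30 | 42% | 21% | 21 | 0.31 |
| 0.50 | 30% | 15% | 15 | 0.19 |

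*Every woman dominant on Day 8 stays dominant in both arms.* The increase rate is presence rate − q. The difference stays at 30 points and both rates drop:

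- q = 0.10: 60 − 10 = 50% vs 30 − 10 = 20%, power 0.57.
- q = 0.20: 60 − 20 = 40% vs 30 − 20 = 10%, power 0.67.

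So the rates fall in both cases whenever q is above zero, while power may fall or rise depending on how far Day 8 dominance persists. The documents give neither q nor persistence. If q is zero, the two definitions coincide.

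**4. Bias.** With no product effect, both arms have the same increase rate under either assumption. A between-arm comparison of increase is therefore unbiased under no effect.

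**The case against.** The strongest reply is that the comparison is already planned. The 11.2 lead-in sets LACTIN-V against placebo, measure 4 in 3.4.1 compares cervicotypes by arm, and 11.5, which governs the analysis, compares the two groups and names a test. The restriction to the LACTIN-V arm in 11.2(1) may attach to Day 64 only. A reader might infer from 11.2(1) that a single-arm analysis is planned; these passages do not support that.

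A second reply is that 3.4.1 labels only presence as its primary outcome, so the Day 8 sentence is background. A reader might also infer that the Day 8 version is invalid. It is not: it is under-defined, but usable if compared between arms. The text sets no binary rule either, so the reading used in the working is one of several.

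Third, the sample size rests on Objective 1 alone, so no design figure depends on this outcome. Section 2.5 says recolonization after antibiotics is often slow, so few women may be dominant on Day 8.

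All of this stands, and it limits the point to one of definition. It does not supply the single definition. In 11.2, Objective 1 ends with a commitment to compare every outcome by arm and Objective 2 has no such line. Section 11.5 names neither the visit nor dominance as its target, and nothing reconciles 4.0 with 3.3.1.

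**Conclusion.** The point holds as an inconsistency in the outcome definition of a primary objective. It should be corrected, and it does not undermine the design.

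Its size can only be illustrated. An assumed 60% on LACTIN-V alone is compatible with a 50-point effect or with none. Under assumed presence of 60% vs 30%, with Day 36 status independent of Day 8, moving from presence to increase lowers the rates to 54% vs 27%, 42% vs 21% or 30% vs 15% as Day 8 dominance goes from 10% to 30% to 50%. Power falls from 0.51 to between 0.43 and 0.19. The direction of the power change is not general, because full persistence of Day 8 dominance would raise it.

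A reader might want to take the likely placebo rate from the Phase 2b trial in section 2.4. The documents do not support that. The trial measured BV recurrence by week 12 after topical metronidazole, with 84% of placebo women evaluable. Absence of BV is also not Lactobacillus dominance in this protocol: BV is Nugent 7-10 (3.4.1), while non-dominance at entry is Nugent 4-10 (5.0).

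**What to change.** Use one outcome for Objective 2 in sections 3.4.1, 11.2 and 11.5: Lactobacillus-dominant cervicotype present at one named primary visit, LACTIN-V versus placebo, in all randomised women. Day 36 would suit, with Day 64 secondary. State the rule that makes a cervicotype dominant. Analyse with the Fisher's exact test already planned, and add the difference in proportions with a 95% CI.

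Then:

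- strike the restriction to the LACTIN-V arm from 11.2(1);
- keep change from Day 8 as a secondary measure, stating the size of increase and how women already dominant on Day 8 are counted;
- use Day 8 dominance as a covariate in a supporting analysis;
- make abundance in 11.5 a separate, secondary comparison;
- align the primary or secondary label in 4.0 with 3.3.1, and add Day 8 to the time points there if it is used.

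The cost is wording. Samples at Days 8, 36 and 64 are already scheduled, and the sample size is unaffected because it rests on Objective 1. The change should be made before unblinding.
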